1.1 Glossary

Term	Definition
AE	Adverse Event
ASIC	Application-Specific Integrated Circuit
BG	Blood Glucose
BLE	Bluetooth Low Energy
BMI	Body Mass Index
CEC	Clinical Events Committee
CFR	Code of Federal Regulations
CGM	Continuous Glucose Monitoring
CIP	Clinical Investigation Plan
CTA	Clinical Trial Agreement
CV	Curriculum Vitae
DKA	Diabetic Ketoacidosis
ECG	Electrocardiogram
eCRF	Electronic Case Report Form
EIS	Electrochemical Impedance Spectroscopy
EMEA	Europe Middle East Africa
EMT	Emergency Medical Technician
EOS	End of Study
ER	Emergency Room
FDA	United States Food and Drug Administration
FST	Frequent Sample Testing
GCP	Good Clinical Practice
GST	Glucose Sensor Transmitter
HIPAA	Health Insurance Portability and Accountability Act of 1996
IB	Investigator's Brochure
ICF	Informed Consent Form
ICR	Insulin to Carb Ratio
ID	Identification
IFU	Instructions for Use
IRB	Institutional Review Board
IV	Intravenous
MC2	Medtronic Core Clinical Solutions
MDI	Multiple Daily Injections
NSR	Non-Significant Risk
OC-RDC	Oracle Clinical Remote Data Capture
PC	Personal Computer
PI	Principal Investigator

Medtronic Business Restricted

Term	Definition
QC	Quality Control
QOL	Quality of life
SADE	Serious adverse device effect
SAE	Serious Adverse Event
SG	Sensor Glucose
SID	Subject Identification
SMBG	Self-Monitoring of Blood Glucose
SOPs	Standard Operating Procedures
TDD	Total Daily Dose
TIR	Time in Range
TS	Technical Support
TLS	Transport Layer Security
UADE	Unanticipated Adverse Device Effect
USB	Universal Serial Bus

1.2 List of Trademarks

Apple Watch™* is a trademark of Apple Inc.

Ascensia, the Ascensia Diabetes Care logo, and Contour are trademarks and/or registered trademarks of Ascensia Diabetes Care.

BodyGuardian® is a trademark of Preventice Technologies Inc.

Fitbit™ is a registered trademark of Fitbit Inc.

The Bluetooth® word mark and logos are registered trademarks owned by Bluetooth SIG, Inc. and any use of such marks by Medtronic is under license.

© 2021 Medtronic. All rights reserved. Medtronic, Medtronic logo and Further, Together are trademarks of Medtronic. Third party brands are trademarks of their respective owners. All other brands are trademarks of a Medtronic company.

2 Synopsis

Title	Use of the Guardian™ Connect system with Smart Connected Devices
Clinical Study Type	Feasibility/Data Collection
Sponsor	Medtronic MiniMed, Inc. ("Medtronic") [name] [contact]
Indication under investigation	Insulin-requiring type 1 and 2 diabetes who use multiple daily injections (MDI) insulin therapy
Devices	
Investigational Devices
 
• Insulin capture devices and associated apps
○ InPen™ Basal smart cap, also referred to as InCap (MMT-155)○ InPen™ Diabetes Management app, Version 6.0.0 by Companion Medical○ Adapter 1 FlexTouch (Levemir, Tresiba) (SPC-00789)○ Adapter 2 KwikPen (Basaglar) (SPC-00790)○ Adapter 3 SoloStar (Lantus) (SPC-00791)○ Adapter 4 SoloStar (Toujeo) (SPC-00792)○ Adapter 5 Max SoloStar (Toujeo Max) (SPC-00793) 
Investigational Devices for Subjects 2-13 Years of Age and 76-80 Years of Age
 
• Guardian™ Connect app• Guardian™ Connect transmitter kit (MMT-7820)
○ Guardian Connect transmitter○ One-press serter, referred to as the serter throughout the protocol○ Tester○ Charger 
FDA Approved Devices Used in an Investigational Manner

Medtronic Business Restricted

	
• Guardian™ Connect app• Guardian™ Connect transmitter kit (MMT-7820)
○ Guardian™ Connect transmitter○ One-press serter, referred to as the serter throughout the protocol○ Tester○ Charger 
Non-Investigational Devices
 
• Guardian™ Sensor (3) (MMT-7020)• Insulin capture devices and associated apps (type, time, amount)
○ Companion Medical InPen for use with Humalog, NovoLog, Fiasp™ U100 (rapid-acting only) (MMT-105)○ InPen™ Diabetes Management App, Version 5.4.4 by Companion Medical• Klue™ Health app by Klue, Inc.• FoodPrint™ food logging app by Nutrino™• Apple Watch™ with Health app• Sleep tracking device such as Fitbit™ tracker• Sponsor-provided smartphone (Android or iPhone) with pre-loaded apps and cellular service• CareLink™ Personal software – referred to as CareLink Personal throughout this protocol• CareLink™ system – referred to as CareLink Professional throughout this protocol• CONTOUR™ NEXT ONE blood glucose meter – referred to as the study meter or BG meter throughout this protocol• CONTOUR™ DIABETES app• BodyGuardian® MINI cardiac remote monitor (BC2003)
Purpose	The purpose of this study is to collect sensor, insulin, sleep, activity and food/meal data for a minimum of 90 days of device wear (Phase 1) and up to a maximum of 9 months of device wear (Phase 2) with optional insulin injection video capture and/or menstrual cycle tracking and/or cardiac monitoring in subjects with insulin requiring diabetes 2-80 years of age.

Objective(s)	The primary objective of this feasibility study is to collect data to be used for development of Medtronic Diabetes and Cardiac Diagnostics devices and products.
Study Design	
The study is a multi-center, prospective single-arm design without controls. All subjects will participate for a minimum of 90 days (Phase 1) and some subjects 18 years of age or older will participate for up to 9 months (Phase 2). All subjects will wear the Guardian Connect system (real-time continuous glucose monitoring (CGM)) continuously and use smart insulin pens or insulin pens with smart caps for multiple daily injections and continue their standard therapy throughout the duration of the study.
 
Once trained, each subject 14 years of age or older or their parent or guardian (if applicable) may insert a sensor in the abdomen or arm. Subjects 2-13 years of age or their parent or guardian may insert a sensor in the abdomen or buttocks.
 
Only subjects 13 years of age and older will wear an Apple Watch (waking hours), a Fitbit (sleeping hours) and have the Klue app.
 
The subject's insulin delivery, sleep, physical activity (as applicable), food intake data, and medication (as applicable) will be collected through applications with meal logging and medication requiring manual entry. In addition, subjects may also participate in optional self-administered insulin injection video capture and upload using BOX and/or monthly menstrual cycle logging using Apple Health and/or cardiac monitoring using BodyGuardian MINI.
 
Only subjects 13 years of age and older who choose to participate in optional video capturing of self-administered insulin injection will use the Klue app on the sponsor-provided smartphone to record insulin injection (capturing two videos per each injection location) any time during the study, and upload videos to BOX on the sponsor-provided smartphone. All other app data will be sent automatically to the cloud throughout study participation. Subjects will also be asked to enable location services on sponsor-provided smartphone throughout the study.
 
Only subjects weighing more than 10 kg who choose to participate in optional cardiac monitoring using BodyGuardian MINI should wear the monitor for a minimum of 14 days.
 
Electronic device data will be collected from the study devices using CareLink Personal software and the FoodPrint app and Nutrino cloud. Each site should create a new CareLink Professional account to review subjects' CGM data. CareLink software uses TLS technology, which encrypts all data it stores (21 CFR Part 11 compliant). Wearables will be reset to factory settings at subject's end of study visit. Sponsor-provided smartphone will be reset to factory settings prior to device return to sponsor.
 
Throughout the study, both in Phase 1 and Phase 2, subjects will continually


Medtronic Business Restricted

	
use the Guardian Connect system, track insulin delivery via the smart pen or pen caps, track sleep, track activity, and respond to prompts (as applicable). Subjects are instructed to use information from the Guardian Connect app in an adjunctive manner, per product labeling. The general study timeline of activities is as follows:
 
Phase 1
 
▪ Day 1-30 
For 7 consecutive days during Days 8-27 (to ensure there is sufficient time for site to review surveillance report prior to Visit 4), each subject should log food consumption (meals, drinks and snacks) concurrent with CGM, sleep and activity tracking, insulin delivery data collection, and medication. The subject will be asked to check a fasting SMBG using the study meter after a minimum of 8 hours of fasting for two mornings during the week they log their food.
 
▪ Day 31-90 
Each subject should log food consumption for a minimum of 7 consecutive days per month.
 
Day 100 will be the End of Study (EOS) unless the subject is participating in Phase 2. If EOS, devices should be returned, wearables reset to factory settings, and subject's participation in the study will be completed.
 
Phase 2
 
▪ Day 91-280 
Some subjects 18 years of age or older will continue to provide data for an additional 180 days based on adherence to study requirements demonstrated during Phase 1. Subjects will be asked to log food consumption (meals, drinks and snacks) for a minimum of 7 consecutive days per month concurrent with CGM, sleep and activity tracking, insulin delivery data collection, and medication. At End of Study (EOS, Day 280 (± 7 Days)) devices should be returned, wearables reset to factory settings and subject's participation in the study will be completed.

Sample Size and Investigational Centers	Up to 500 subjects with insulin-requiring type 1 or type 2 diabetes age 2-80 who use multiple daily injections (MDI) insulin therapy will be enrolled in the study in order to have a minimum of 260 subjects complete 90 days of data collection with some adult subjects completing 280 days. Up to 30 investigational centers will be selected across the United States. Selection is based on each investigator's experience and qualifications, availability of sufficient resources to carry out the required study procedures, and the investigator's ability to recruit subjects into the study.
Duration	The study is anticipated to last approximately 24 months from first investigational center initiation to finalization of all data entry and monitoring procedures. Subject participation is expected to be

	approximately 100 days, and approximately 280 days for adult subjects who complete Phase 2.
Inclusion/ Exclusion Criteria	
Inclusion Criteria
 
1. Individual is 2-80 years of age at time of consent.2. A clinical diagnosis of type 1 or type 2 diabetes as determined by investigator for:
o at least the last 6 months for subjects 2-6 years of ageo at least the last 12 months for subjects 7-80 years of age3. Subject is on multiple daily injection therapy (3 or more insulin injections per day one of which is a long acting insulin injection), is currently using or is willing and can afford to use insulin pen(s) and pen cartridge(s).4. Subject is currently using or is willing to use the Guardian Connect system during the study.5. Subject agrees to comply with the study protocol requirements.6. For adult subjects: Subject is capable of providing legal consent without a legal authorized representative. 
Exclusion Criteria
 
1. Subject is using a syringe and unwilling or unable to use insulin pen(s).2. Subject is using an insulin pump.3. Subject is currently using a non-Medtronic standalone CGM system and unwilling to use only the Guardian Connect system during the study.4. Subject is using hydroxyurea at time of screening or plans to use it during the study.5. Subject will not tolerate tape adhesive in the area of device placement as assessed by a qualified provider.6. Subject has any unresolved adverse skin condition in the area of device placement (e.g. psoriasis, rash, Staphylococcus infection).7. Subject is actively participating in or plans to enroll in an investigational study (e.g. drug or device), other than this study, wherein they have received treatment from an investigational drug or device.8. Subject has a positive urine pregnancy test at time of screening.

Medtronic Business Restricted

	
9. Subject is female, sexually active without the use of contraception, able to become pregnant or plans to become pregnant during the course of the study.
 
10. Subject is unwilling to participate in study procedures.
 
11. Subject is directly involved in the study as research staff.

Study Visit Schedule	
Subjects will participate in a minimum of 6 planned study visits, as presented in Figure 1 for approximately 90 days of device wear and up to 12 planned study visits (up to 9 months of device wear) for some adult subjects participating in Phase 2. Telehealth (phone or video) visit may be performed for office visits in cases where an office visit is not possible (e.g. global pandemic).
 
Phase 1
 
▪ Visit 1 Enrollment (Office): Consent and screening.
○ Administer baseline questionnaire▪ Visit 2 Day 1 Device on Body (Office): (up to 14 days after Visit 1*): Study, device and app training.
○ Setup app settings, ensuring subjects accept app terms and conditions○ Guardian Connect system start, including sensor insertion, and training○ Provide app and wearables training○ Dispense wearables○ Dispense study supplies○ Discuss and determine target date for completing one 7-day consecutive meal logging during Days 8-27, prior to Visit 4 
*Note: If additional time is needed for training, Visit 2 may be split up into two visits at investigator's discretion. Site should complete an "Unscheduled Visit" eCRF to document additional visit.
 
▪ Visit 3 Day 10 Follow-up (Phone): Day 10 (± 4 days) after Visit 2.
○ Remind subjects to have continuous sensor wear○ Remind subject to complete 7-day consecutive meal logging on targeted dates prior to Visit 4○ Based on data surveillance reports as available (provided by sponsor), discuss subject compliance (e.g. meal logging, CGM use, sleep and insulin tracking etc.)

- Visit 4 Day 30 Follow-up (Office): Day 30 (± 7 days) after Visit 2.
 - Dispense study supplies
 - Based on data surveillance reports as available (provided by sponsor), discuss subject compliance (e.g. meal logging, CGM use, sleep and insulin tracking etc.)
 - Discuss and determine target date for completing one 7-day consecutive meal logging prior to Visit 5
- Visit 5 Day 60 Follow-up (Office or Phone): Day 60 (± 7 days) after Visit 2.
 - If subject is participating in cardiac monitoring:
 - Train subject on cardiac monitor
 - Dispense cardiac monitor and supplies
 - Based on data surveillance reports as available (provided by sponsor), discuss subject compliance (e.g. meal logging, CGM use, sleep and insulin tracking etc.)
 - Discuss and determine target date for completing one 7-day consecutive meal logging prior to Visit 6
 - Determine if subject will participate in Phase 2
 - If not participating in Phase 2, determine Day 90 when subject may stop data collection and schedule Visit 6 (EOS)
- Visit 6 (Office): Day 100 (± 7 days) after Visit 2.
 - If EOS:
 - Return study meter, transmitter, wearables and sponsor-provided smartphone
 - Wipe data off (perform factory reset) wearables
 - Administer EOS questionnaire

Note: EOS questionnaires will be administered to all subjects at the end of their participation in the study. This includes subjects who are terminated or who voluntarily discontinue participation in the study.
 - If moving onto Phase 2, see below.

Phase 2: Subjects participating in study for over 90 days (up to 9 months):

- Visit 6 Day 90 Follow-up (Office): Day 90 (± 14 days) after Visit 2.
 - Dispense study supplies.
 - Based on data surveillance reports as available (provided by sponsor), discuss subject compliance (e.g. meal logging, CGM use, sleep and insulin tracking etc.)

[figure not shown]
	
○ Discuss and determine target dates for completing one 7-day consecutive meal logging prior to Visit 7 ▪ Visit 7 Day 120 Follow-up (Phone): Day 120 (± 14 days) after Visit 2.
○ Based on data surveillance reports as available (provided by sponsor), discuss subject compliance (e.g. meal logging, CGM use, sleep and insulin tracking etc.)○ Discuss and determine target date for completing one 7-day consecutive meal logging prior to Visit 8 ▪ Visit 8 Day 150 Follow-up (Phone): Day 150 (± 14 days) after Visit 2.
○ Based on data surveillance reports as available (provided by sponsor), discuss subject compliance (e.g. meal logging, CGM use, sleep and insulin tracking etc.)○ Discuss and determine target date for completing one 7-day consecutive meal logging prior to Visit 9 ▪ Visit 9 Day 180 Follow-up (Office): Day 180 (± 14 days) after Visit 2.
○ Dispense study supplies.○ Based on data surveillance reports as available (provided by sponsor), discuss subject compliance (e.g. meal logging, CGM use, sleep and insulin tracking etc.)○ Discuss and determine target dates for completing one 7-day consecutive meal logging prior to Visit 10 ▪ Visit 10 Day 210 Follow-up (Phone): Day 210 (± 14 days) after Visit 2.
○ Based on data surveillance reports as available (provided by sponsor), discuss subject compliance (i.e. meal logging, CGM use, sleep and insulin tracking etc.)○ Discuss and determine target date for completing one 7-day consecutive meal logging prior to Visit 11 ▪ Visit 11 Day 240 Follow-up (Phone): Day 240 (± 14 days) after Visit 2.
○ Based on data surveillance reports as available (provided by sponsor), discuss subject compliance (e.g. meal logging, CGM use, sleep and insulin tracking etc.)○ Discuss and determine target date for completing one 7-day consecutive meal logging prior to Visit 12○ Determine date for Day 280 when subject may stop data collection and schedule Visit 12 (EOS) ▪ Visit 12 End of study (EOS) (Office): Day 280 (± 7 days) after Visit 2.
--	--

Medtronic Business Restricted

	
○ Administer EOS questionnaire Note: EOS questionnaires will be administered to all subjects at the end of their participation in the study. This includes subjects who are terminated or who voluntarily discontinue participation in the study.○ Return study meter, transmitter, wearables and sponsor-provided smartphone○ Wipe data off (perform factory reset) wearables
--	---

Medtronic Business Restricted

Figure 1. Study Visit Schedule for Phase 1 and Phase 2, 90 Days and 280 Days of Guardian Connect system Wear

Safety and Monitoring/Risk Analysis	Safety monitoring/risk analysis details are outlined in Section 10 .
Device Deficiencies	Device deficiencies reported directly to the investigational center staff by a subject should either be reported to the Medtronic support line by the subject or investigational center staff. All applicable device deficiencies that are reported to the Medtronic support line will be documented. Depending on the study device or app, the subject and/or investigational center may be instructed by the support line to contact the respective device manufacturer. Device deficiencies for commercially released devices or apps should be captured according to local regulatory requirements and is the responsibility of the Investigator. For additional information, see Section 11.8 .
Subject Stopping Rules	Refer to Section 9.10 on “Subject Exit, Withdrawal or Discontinuation”.
Study Stopping Rules for Entire Study	There are no predefined study stopping rules.

Statistical Analysis for Endpoints and Hypothesis	
During Phase 1 and Phase 2
 
Primary Endpoint Descriptive statistics will be performed; no statistically powered analyses or hypothesis testing will be performed.
 
• Glycemic control: Percentage of Time in Range (SG <70 mg/dL, 70-180 mg/dL, and >180 mg/dL) 
Other Descriptive Endpoints
 
• Summary of completed data collection/available data• Summary of study questionnaire results 
Safety Descriptive summary will be used to characterize safety events:
 
• Serious adverse events (SAE)• Device related adverse events (AEs)• Procedure related AEs• Serious adverse device effect (SADE)• Unanticipated adverse device effect (UADE)• Severe hypoglycemia• Diabetic ketoacidosis (DKA) 
Device Deficiencies Descriptive summary will be used to characterize device deficiencies.

Final Report	A final report will be generated once all subjects have completed Phase 1 and Phase 2. Descriptive endpoints and safety data will be summarized and presented in the final report.

3 Introduction

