7.1 Study Population

Up to 500 subjects with insulin-requiring type 1 or type 2 diabetes age 2-80 who use multiple-daily injections (MDI) insulin therapy will be enrolled in the study in order to have minimum of 260 subjects complete approximately 100 days of study participation with some adult subjects completing approximately 280 days in Phase 2.

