Dispense cardiac monitor and supplies. Train subjects on the use of cardiac monitor.					x (if applicable)								
Instruct subject to contact the investigational center staff in the event they experience problems with their study devices (refer to Section 11.8).		x											
Assess subjects for the occurrence of any adverse events or device deficiencies (see Section 11) at each visit and document on the appropriate source and record event(s) on the appropriate eCRF.		x	x	x	x	x	x	x	x	x	x	x	x
Based on data surveillance reports as available (uploaded to BOX by sponsor), discuss subject compliance (e.g. meal logging, CGM use, sleep and insulin tracking etc.)			x	x	x		x	x	x	x	x	x	
Schedule next visit/phone call date and time.	x	x	x	x	x		x	x	x	x	x	x	

Medtronic Business Restricted

CIP331 Clinical Investigation Plan

D00323255

Version

Page 48 of 78

Medtronic

	Phase 1						Phase 2						
	Visit 1 (Office)	Visit 2 (Office)	Visit 3 (Phone)	Visit 4 (Office)	Visit 5 (Office or Phone)	Visit 6, EOS (Office)	Visit 6 (Office)	Visit 7 (Phone)	Visit 8 (Phone)	Visit 9 (Office)	Visit 10 (Phone)	Visit 11 (Phone)	Visit 12, EOS (Office)
Visit Window	Enrollment	Up to 14 Days After Visit 1	Day 10 (± 4 Days) After Visit 2	Day 30 (± 7 Days) After Visit 2	Day 60, Day 60 (± 7 Days) After Visit 2	Day 100 (± 7 Days) After Visit 2	Day 90, (± 14 Days) After Visit 2	Day 120 (± 14 Days) After Visit 2	Day 150 (± 14 Days) After Visit 2	Day 180 (± 14 Days) After Visit 2	Day 210 (± 14 Days) After Visit 2	Day 240 (± 14 Days) After Visit 2	Up to Day 280 (± 7 Days) After Visit 2
Discuss and schedule with subject the targeted 7-consecutive days of meal logging to occur before next.		x		x	x		x	x	x	x	x		
Determine if subject will participate in Phase 2				x									
Return cardiac monitor and supplies						x (if applicable)							
Return study devices, unused supplies, and study guides from subject (Refer to Table 1)						x							x
Administer EOS questionnaire					x								x
An Exit eCRF will be completed at this visit. The investigational center staff will complete the Exit eCRF even if the study devices are not worn for the required time or if the subject self-removed one or more study devices at home.					x								x
Enter data into eCRFs as appropriate.	x	x	x	x	x	x	x	x	x	x	x	x	x
General Reminders													
Inform subject that observation or assistance by sponsor may occur at any time during the study	x												
Remind subject to bring insulin pen to Visit 2	x												

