9.10 Subject Exit, Withdrawal or Discontinuation

Subjects may choose to withdraw from the study at any time by notifying investigational center staff of their intent.

If a subject chooses to end his or her study participation or if the subject is removed from the study at the Investigator's discretion or for failure to meet the study requirements, the reason for withdrawal

Medtronic Business Restricted

must be documented. All study devices and supplies must be returned (as applicable) and documented both in source documents and on an eCRF.

Subjects may also be withdrawn from the study at the discretion of the Investigator. A subject will be withdrawn from the study if:

- In the opinion of the investigator, the subject's health or safety would be compromised by continuing in the study
- In the opinion of the investigator, it is in the subject's best interest to discontinue participation in the study
- During the course of the study, subject begins participation in another investigational study (drug or device).
- The subject is found to no longer meet all inclusion criteria, or is found to meet one or more exclusion criteria
- The subject fails to comply with one or more study requirements
- During the study, (female) subject becomes pregnant.

Documentation of the reason(s) leading to subject withdrawal will be kept in the subject's source documentation.

Medtronic Business Restricted

10 Risks and Benefits

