## **7. Statistical Methods**

### **7.1 Study Subjects**

#### **7.1.1 Disposition of Subjects**

The number of subjects screened, enrolled, completed and withdrawn in the study will be presented. The reasons for subject's withdrawal will be summarized.

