#### **7.1.3 Analysis Sets**

All enrolled subjects will be included in the safety analysis population.

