### **7.4 Handling of Missing, Unused, and Spurious Data and Dropouts**

In the case of partially missing day and/or month, the first day of the month will be used for event dates with known year and month but unknown day, unless specified otherwise in the description; similarly, the first day of the year will be used for event dates with known year but unknown month and day, unless specified otherwise.

In the case of partially missing time, 12am will be used for event times with known day but unknown time, if applicable.

No additional imputation will be applied for the missing data.

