## 7.9 Evaluation of Objectives

### 7.9.1 Endpoints

Descriptive statistics will be performed; no statistically powered analyses or hypothesis testing will be performed.

- Glycemic control: Percentage of Time in Range (SG <70 mg/dL, 70-180 mg/dL, and >180 mg/dL)

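### Does it matter that the 260-completer target is worded two ways and that the SAP names no analysis set for Time in Range?

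*Protocol*

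**What the plan says.** **The target.** The sample-size row of the Protocol Synopsis enrols up to 500 subjects "in order to have a minimum of 260 subjects complete 90 days of data collection with some adult subjects completing 280 days". Protocol section 7.1 gives the same purpose as a "minimum of 260 subjects complete approximately 100 days of study participation with some adult subjects completing approximately 280 days in Phase 2". Protocol section 13.4 and SAP section 6 repeat the cap of 500 and omit the 260.

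**Completion.** SAP section 7.1.1 states: "The number of subjects screened, enrolled, completed and withdrawn in the study will be presented". It sets no data threshold. The visit table in Protocol section 9.2 says that site staff "will complete the Exit eCRF even if the study devices are not worn for the required time". Protocol section 9.10 lists among the grounds for withdrawal: "The subject fails to comply with one or more study requirements". SAP section 5 refers the reader to Protocol section 5, where participation ends at the end-of-study visit: Day 100, or Day 280 for those who continue.

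**The endpoint.** SAP section 7.9.1 has one line, "Glycemic control: Percentage of Time in Range (SG <70 mg/dL, 70-180 mg/dL, and >180 mg/dL", after stating that the work is descriptive, with no powered analysis and no test. The only analysis set is in SAP section 7.1.3: "All enrolled subjects will be included in the safety analysis population". Apart from rules for partial dates and times, SAP section 7.4 says: "No additional imputation will be applied for the missing data". SAP section 7.9.2 and Protocol sections 4.2.1 and 13.7 also plan a summary of how much data were collected and are available.

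**Phase 2 end.** Protocol section 5 has continuing subjects supply data for a further 180 days under a heading of Day 91 to 280. The Synopsis puts maximum wear at 9 months. Visit 11 in section 9.1.1 fixes Day 280 as the point at which data collection may stop.

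**The concern.** The stated objective is to collect data, and 260 is the only completer number in the plan. One wording sounds like an amount of data, the other like calendar time to the exit visit. A subject with 90 days of data who misses Visit 6 meets only the first. A subject who attends Visit 6 after long sensor gaps may meet only the second, and the exit-form instruction shows that the protocol foresees short wear. If 90 days of data collection means 90 days with data, 260 completers would supply 260 × 90 = 23,400 subject-days, whereas the participation wording guarantees no amount.

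The Time-in-Range line raises a second doubt. Enrolment is signature of consent (Protocol section 7.2), before any sensor is placed at Visit 2. The safety set can therefore include people with no sensor glucose and cannot serve unchanged as the denominator. Nothing says whether non-completers' readings count, whether the phases are combined, or whether readings are averaged within subject first. At stake would be the disposition count and the reading of the primary summary.

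**Working it through.** **1. Reproducing the target.** No formula can be reproduced, because the documents give no precision target, SD, power or dropout rate. The arithmetic is 260/500 = 52% completion, so at most 500 − 260 = 240 subjects (48%) could fail to complete. The 500 is a cap, which makes 240 a ceiling and not a forecast.

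**2. The two wordings against the schedule.** For subjects who do not continue, Protocol section 9.1.1 lets data collection stop at Day 90 and places the exit visit at Day 100 ± 7, that is Day 93 to Day 107. The Synopsis itself holds both figures: 90 days of data collection in the sample-size row and participation of about 100 days in the Duration row. The number is 260 in both places. A subject who follows the schedule stops collecting at Day 90, exits near Day 100 and satisfies both.

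**3. Is there a subject-day shortfall?** Assume participation completers have data on 60%, 75% or 90% of the 90 days (the documents give no wear rate). Then 23,400 × 0.60 = 14,040, × 0.75 = 17,550 and × 0.90 = 21,060 subject-days. These are shortfalls only if the Synopsis requires 90 days with data. It need not. Section 9.1.1 describes Phase 1 as about 90 days of wear and treats data collection as an activity that stops on a date. Read as a period, neither wording promises an amount of data, and the shortfall disappears. No subject-day target appears in either document.

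**4. How far the counts could differ.** If 5%, 10% or 20% of subjects who meet one reading fail the other (assumed), 260 becomes 260 × 0.95 = 247, 260 × 0.90 = 234 or 260 × 0.80 = 208. No test, precision statement or decision rule uses the count.

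**5. Effect of the analysis set on mean Time in Range.** Let k non-completers have sensor data and let their mean differ from that of 260 completers by g points. Including them moves the mean by g × k/(260 + k).

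| k (assumed) | Shift per point of g |
|---|---|
| 60 | 60/320 = 0.19 |
| 120 | 120/380 = 0.32 |
| 240 (ceiling) | 240/500 = 0.48 |

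The documents do not give g. With g assumed at 5 to 10 points, the ceiling case gives 0.48 × 5 = 2.4 to 0.48 × 10 = 4.8 points. If 10% of the subjects summarised were non-completers, the shift would be 0.10 × 5 = 0.5 to 0.10 × 10 = 1.0 points. Neither mean is wrong: they describe different groups.

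**6. Phase 2 end.** Day 90 + 180 = Day 270. Day 91 to Day 280 is 280 − 91 + 1 = 190 days. The difference is 10 days, and 10/190 = 5.3%. Nine calendar months are 273 to 276 days, which lies between the two. For a subject summarised over Phase 2 alone, including the last 10 days moves the percentage by 10/190 = 0.053 points per point of difference between those days and the preceding 180.

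**The case for a change.** The strongest case for acting is that the sponsor could choose the counting rule after seeing the data, and that a few sentences would prevent it at no cost in subjects or visits. Phase 2 subjects are adults selected for adherence in Phase 1. If readings were pooled across subjects, someone followed for 280 days would carry 280/90 = 3.1 times the weight of someone followed for 90. For subjects who continue, Visit 6 is at Day 90 ± 14, so no visit marks their hundredth day.

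Part of this stands. The two target sentences do differ, SAP section 7.9.1 is silent on set, window and unit, and the Phase 2 wordings disagree on the last day of data.

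The rest weakens on inspection. Completion has a schedule meaning through the SAP's reference to Protocol section 5. The exit-form instruction requires a form when wear is short; it does not make that subject a completer. Withdrawal for non-compliance tends to bring the two counts together. Data volume is reported apart from disposition, so poor wear behind a good attendance count should be visible. Pooling readings across subjects is possible under the text, but it is not how an analyst would ordinarily compute a percentage of time for a group of people.

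**Conclusion.** The gaps are real but are ones that analysts fill sensibly, and no change to the plan is needed. The two target sentences describe the same 260 subjects at two points of one schedule, and no success criterion or test depends on which is used. For Time in Range, subjects without sensor glucose have no percentage to contribute. With no imputation planned, the natural summary is each subject's percentage over available data, described across subjects who have any, with the number shown. The planned summary of available data lets the reader judge completeness.

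The largest conceivable effect of the choice of subjects is 0.48 points per point of gap. It requires full enrolment of 500, the maximum 240 non-completers, and sensor data from all of them; the gap itself is unknown. The endpoint is descriptive, so this affects how a mean is read and no error rate.

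The Phase 2 mismatch is a clerical slip of 10 days in an optional adult subset. The passages should agree whenever the protocol is next edited, but no analysis turns on it.

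This conclusion rests on the study remaining descriptive and on the report stating the number of subjects behind each summary.
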